3.3. Inclusion Criteria

Subjects must meet the following criteria to be selected for participation in the study:

- 22 years of age or older
- Scheduled for PICC insertion using the G4 system
- Willing to allow thoracic photos to be obtained after ECG lead placement

3.4. Exclusion Criteria

Subjects who meet any of the following criteria are not eligible for participation in the study:

- < 22 years of age
- Patient has a pacemaker
- Patient condition precludes ECG use and lead placement
- Patient condition precludes radiographic imaging
- Unwilling to allow thoracic photos to be obtained after ECG lead placement

4. Study Procedures

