3.1. Participant Population

Adult male patients scheduled to receive a PICC insertion using the G4 tip navigation system may be considered for participation in the study.

As this is a feasibility study, male and female patients will be recruited for participation in this study. As a means to limit female exposures to photographs, Images will only be captured for male subjects

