4.2. Screening and Enrollment

After the informed consent document has been signed, the subject will undergo screening procedures. All subjects screened for the study will be entered on the Screening/Enrollment Log and sequentially assigned a subject identification number. Present diagnosis requiring PICC placement and cardiovascular disease history, including pacemaker, and/or a history of arrhythmic heart conditions such as: atrial fibrillation, atrial flutter, severe tachycardia, or pacemaker driver rhythms will be captured for all subjects enrolled. Subjects who do not meet all inclusion/exclusion criteria will not be enrolled in the study. The reasons for screening failure will be documented on the screening/enrollment log.

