4.3. ECG Lead Placement Image Capture

ECG lead will be placed according to the standardized ECG lead placement chart below. A second study team member will confirm and attest to the proper placement of the ecg lead in accordance with the ECG lead placement chart below. For some male subjects who consent, the placement of thoracic ECG leads will be documented by three photographs: one photo capturing the chest perpendicular to the xiphoid process, and one left and right oblique photograph. A ruler should be placed in the photograph, not obscuring any ECG leads, as a scale reference. Images captured will exclude portions of the body above the shoulders.

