4.3.1. ECG Lead Placement and Procedure

The subject identification number will be entered into the ECG machine to ensure the correct subject data can be identified. (See below for ECG lead placement.)

ECG 12 lead placement:

Standardized placement of ECG leads is important. ECG lead placement must be consistent between subjects and performed according to the directions provided in this section below. Primary and secondary ecg lead placement attestation will be used to document the lead placement for each subject, to confirm the accuracy of the lead placement with the requirements of the protocol. Some consenting male subjects will undergo photographic documentation of ECG leads.

ECG Lead	Anatomical Placement
Lead 1	Fourth intercostal space on the right sternum
Lead 2	Fourth intercostal space on the left sternum
Lead 3	Midway between placement of Lead 2 and Lead 4 fifth intercostal space at the midclavicular line
Lead 4	Fifth intercostal space at the left and mid clavicular line
Lead 5	Anterior axillary line on the same horizontal level as Lead 4
Lead 6	Mid axillary line on the same horizontal level as Lead 4 and Lead 5
Right Arms (RA)	Anywhere between the right shoulder and right elbow
Right Leg (RL)	Anywhere between the right torso and the right ankle
Left Arm (LA)	Anywhere between the left shoulder and the left elbow
Left Leg (LL)	Anywhere between the left torso and the left ankle

Note: There will be three "duplicate" electrodes (RA / LA and RL) between the two systems (G4 and 12-lead ECG). Duplicate electrodes should be placed as close together as possible without interfering with the other electrode.

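### Sections 3.3 and 3.4 make willingness to have thoracic photographs an entry condition for women as well as men, although section 3.1 says only men are photographed

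*Combined protocol and SAP*

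**What the plan says.** **Entry criteria.** Section 3.3 requires each subject to be "Willing to allow thoracic photos to be obtained after ECG lead placement". Section 3.4 excludes anyone "Unwilling to allow thoracic photos to be obtained after ECG lead placement". Section 4.2 makes both binding: "Subjects who do not meet all inclusion/exclusion criteria will not be enrolled in the study".

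**Who is recruited and who is photographed.** Section 3.1 opens with men only: "Adult male patients scheduled to receive a PICC insertion using the G4 tip navigation system may be considered for participation". It then says that "male and female patients will be recruited for participation in this study", and adds: "As a means to limit female exposures to photographs, Images will only be captured for male subjects". Section 4.3 narrows photography further: "For some male subjects who consent, the placement of thoracic ECG leads will be documented by three photographs". Section 4.3.1 repeats this: "Some consenting male subjects will undergo photographic documentation of ECG leads".

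**How lead placement is recorded.** Sections 4.3 and 4.3.1 have a second team member confirm placement. Under 4.3.1, primary and secondary attestation documents placement for each subject, photographed or not.

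**Text that points the other way.** The synopsis and section 2.1 list photographs within the primary endpoint. Section 2.2 gives photographic documentation to everyone enrolled. Section 3.2 makes it a condition of being evaluable, and section 7.2.2 drops non-evaluable subjects from the feasibility population. Section 6 describes the thoracic photograph as something that will be taken, without restriction to men.

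**The concern.** An eligibility rule should exclude people who cannot or will not do what the study asks of them. Here the rule applies to women, of whom the study asks no photograph. Two things are at stake.

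- **Consent and privacy.** Section 3.1 restricts images to men in order to limit women's exposure to photography. A woman must nevertheless state that she is willing to be photographed before she can enter. A consent discussion cannot coherently present the photographs both as a condition of entry and as something that will not be done to her.
- **Recruitment.** Otherwise suitable candidates can be turned away for a reason with no stated link to the correlation between intravascular and extravascular ECG recordings.

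The rule acts at screening, before the evaluability definition in 3.2 comes into play. Correcting 3.2 alone would leave these candidates excluded.

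**Working it through.** The plan has no figure to reproduce here; section 7.1 says the sample size is not statistically justified. The check is to apply the sections, as written, to each kind of candidate.

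| Candidate | Eligible under 3.3, 3.4 and 4.2? | Photographed under 3.1, 4.3 and 4.3.1? | Evaluable under 3.2? |
|---|---|---|---|
| Woman, willing | Yes | No | No |
| Woman, unwilling | No, screen failure | Would not have been | Not reached |
| Man, willing | Yes | Some are | Only if photographed |
| Man, unwilling | No, screen failure | Would not have been | Not reached |

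1. **Women.** The second row is the contradiction. The only criterion she fails concerns a procedure that 3.1 rules out for her.
2. **Does the opening of 3.1 remove the problem?** If only men could enter, the criterion would never reach a woman. But the next sentence of 3.1 recruits both sexes, and a rule to limit women's exposure to photographs has no purpose if there are no women. The men-only opening is therefore part of the inconsistency and does not resolve it.
3. **Men.** Requiring every man to be willing and then photographing only some of them is coherent. The tension lies in the reference to those who consent, which suggests that a man could decline and stay in. The consent pages are not in the text reviewed, so how consent to photography is taken cannot be seen.
4. **Is the criterion needed to document placement?** Not under 4.3.1, where two-person attestation does this for each subject.
5. **Would deleting the two bullets be enough?** No. People who decline photographs would then enrol, be non-evaluable under 3.2 and be dropped under 7.2.2. Enrolment of up to 30 for 20 evaluable leaves 30 − 20 = 10 places for non-evaluable subjects, and each such person would use one. Willing women already would, by the first row.
6. **Size.** Let f be the share of women among candidates, and r_w and r_m the proportions of women and men who are unwilling. The proportion lost is f·r_w + (1 − f)·r_m. The share of women among those eligible is f(1 − r_w) / [f(1 − r_w) + (1 − f)(1 − r_m)]. The documents give none of f, r_w or r_m. If r_w = r_m, the share of women stays at f; if both are 0, nobody is lost. Neither quantity can be narrowed from the text.

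**The case against.** The strongest reply is that photographs are required data. They are in the primary endpoint (synopsis, 2.1), section 2.2 provides them for everyone enrolled, and 3.2 makes them a condition of evaluability. On that reading a willingness criterion is sensible, and calling the exclusions pointless ignores what the study set out to collect. This stands to the extent that the plan is in conflict over whether photographs are mandatory, and the entry criteria are one symptom. It does not rescue the criterion for women, because 3.1 expressly rules out images of them.

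Three stronger readings are tempting and are not supported.

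- **That the criterion is equally contradictory for men.** It is awkward, but asking all men to be willing and photographing some is a possible design.
- **That a sizeable share of candidates is lost, or that women end up under-represented.** This needs refusal rates and a sex mix that the documents do not give. A woman told that no images of women are taken may have little reason to refuse. Nor does the plan say that women were admitted to secure their representation; 3.1 refers only to this being a feasibility study.
- **That the ECG correlation is biased.** Nothing in the documents links willingness to be photographed with the recordings, and no analysis by sex is planned.

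It is also fair to say that screen failures do not use up the 30 enrolment places. Their cost is recruitment effort.

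**Conclusion.** The point holds for women. As written, sections 3.3, 3.4 and 4.2 screen out a woman who declines photographs that section 3.1 says will not be taken of her. For men it is a tension with 4.3 and 4.3.1 that needs clarifying, short of a contradiction. The conclusion assumes that women are recruited, as the second sentence of 3.1 says.

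The size is unknown and cannot be derived from the documents. The screening log may not reveal it fully either: under 4.1 staff approach people already thought to be eligible, while 4.2 begins screening after consent is signed, so refusals at the approach may go unrecorded. The defect concerns who may enter and what they are asked to agree to. It is not shown to affect safety or the validity of the ECG comparison, but it should be corrected because the rule contradicts the plan's own privacy provision and is cheap to change.

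**What to change.** - Remove the photo bullets from 3.3 and 3.4 or, at minimum, limit them to men who are to be photographed.
- Record photography at consent as an opt-in for men, and state that declining does not affect eligibility.
- Keep the two-person attestation in 4.3 and 4.3.1 as the lead-placement record for every subject.
- In the same amendment, align the synopsis, 2.1, 2.2, the opening sentence of 3.1, the evaluability definition in 3.2 (and through it 7.2.2) and the photograph text in section 6, so that attestation satisfies the lead-placement requirement. Without this step, newly eligible women and unphotographed men would enter and then be excluded from the feasibility population.

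The cost is a wording amendment to the protocol and consent form, with IRB approval under 10.3. The downside is that fewer men may be photographed, so there may be fewer images to set beside the attestation.

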4.1. Informed Consent

Subjects being scheduled to receive a PICC will be approached by clinical staff if deemed to meet the eligibility criteria for the study. Consent for participation in the study will be obtained from the subject using an Institutional Review Board (IRB) approved informed consent form (ICF) after study aims, methods, benefits and risks have been fully explained by the investigator or member of the study staff. Participation in the study is voluntary and the subject may withdraw at any time. Subjects will be told that electing not to participate in this study will not affect the care received for treatment. The subject will have a private room with sufficient time to read the informed consent form and ask any questions. A copy of the fully executed informed consent form will be given to the subject.

4.2. Screening and Enrollment

After the informed consent document has been signed, the subject will undergo screening procedures. All subjects screened for the study will be entered on the Screening/Enrollment Log and sequentially assigned a subject identification number. Present diagnosis requiring PICC placement and cardiovascular disease history, including pacemaker, and/or a history of arrhythmic heart conditions such as: atrial fibrillation, atrial flutter, severe tachycardia, or pacemaker driver rhythms will be captured for all subjects enrolled. Subjects who do not meet all inclusion/exclusion criteria will not be enrolled in the study. The reasons for screening failure will be documented on the screening/enrollment log.

4.3. ECG Lead Placement Image Capture

ECG lead will be placed according to the standardized ECG lead placement chart below. A second study team member will confirm and attest to the proper placement of the ecg lead in accordance with the ECG lead placement chart below. For some male subjects who consent, the placement of thoracic ECG leads will be documented by three photographs: one photo capturing the chest perpendicular to the xiphoid process, and one left and right oblique photograph. A ruler should be placed in the photograph, not obscuring any ECG leads, as a scale reference. Images captured will exclude portions of the body above the shoulders.

4.3.1. ECG Lead Placement and Procedure

The subject identification number will be entered into the ECG machine to ensure the correct subject data can be identified. (See below for ECG lead placement.)

ECG 12 lead placement:

Standardized placement of ECG leads is important. ECG lead placement must be consistent between subjects and performed according to the directions provided in this section below. Primary and secondary ecg lead placement attestation will be used to document the lead placement for each subject, to confirm the accuracy of the lead placement with the requirements of the protocol. Some consenting male subjects will undergo photographic documentation of ECG leads.

ECG Lead	Anatomical Placement
Lead 1	Fourth intercostal space on the right sternum
Lead 2	Fourth intercostal space on the left sternum
Lead 3	Midway between placement of Lead 2 and Lead 4 fifth intercostal space at the midclavicular line
Lead 4	Fifth intercostal space at the left and mid clavicular line
Lead 5	Anterior axillary line on the same horizontal level as Lead 4
Lead 6	Mid axillary line on the same horizontal level as Lead 4 and Lead 5
Right Arms (RA)	Anywhere between the right shoulder and right elbow
Right Leg (RL)	Anywhere between the right torso and the right ankle
Left Arm (LA)	Anywhere between the left shoulder and the left elbow
Left Leg (LL)	Anywhere between the left torso and the left ankle

Note: There will be three "duplicate" electrodes (RA / LA and RL) between the two systems (G4 and 12-lead ECG). Duplicate electrodes should be placed as close together as possible without interfering with the other electrode.

4.4. PICC Insertion, ECG, Chest X-ray, and Data Collection

The ECG recording and chest x-ray will be performed as described in the sections below. The ECG machine should start recording data prior to the first skin puncture and continue recording through catheter tip placement.

The study staff will defer to the institution's policy for confirming proper tip placement.

After successful PICC tip placement , ECG data collection can be terminated. Up to a maximum of 10 subjects in whom the blue bull's eye was not achieved during PICC navigation will be included as evaluable subjects. Beyond, these 10 subjects, **if the blue bull's eye is not achieved the subject's participation in the study will be terminated and no additional study procedures will be performed.** If an ECG lead should fall off during the data collection period, the lead can be replaced, as long as, the G4 system is not displaying the orange caution indicator on the screen. If the caution indicator is displayed refrain from replacing the lead. If the ECG stops recording during the data collection period, it will not be resumed.

Data Collection Procedures

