3.2. Sample Size

A sample size of up to 30 adult subjects will be enrolled to obtain 20 evaluable subjects. Including a maximum of 10 subjects in whom the G4 system was used for tip navigation but the blue bull's eye was not achieved and 10 subjects where the blue bull's eye served as confirmation for tip placement. An adult subject per The Federal Food, Drug, and Cosmetic Act (FD&C Act) is persons 22 years of age and older at the time of treatment.^{vi} To be considered an evaluable subject, data must be collected for the duration of the PICC insertion procedure on both the G4 and the ECG machines, the post-insertion chest x-ray completed, and photographic documentation of the ECG lead placement captured. Non-evaluable subjects will be replaced to meet the target sample size.

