4.6.1. Completed Study

Subject is considered to have completed the study after completion of all study procedures.

4.6.2. Subject Initiated Early Termination from Study:

A subject's participation in the study will be immediately terminated upon subject withdrawal of consent. Upon termination a final AE assessment should be performed by the study staff.

4.6.3. Investigator Initiated Early Termination from Study:

If the Investigator feels that the subject can no longer fully comply with the requirements of the study, if any of the study procedures would not be in the best interest of the subject, or if any of the study procedures cannot be completed on the subject (data collection on 12-lead

ECG and/or chest x-ray) the investigator should withdraw the subject from the study. Upon termination a final AE assessment should be performed by the study staff.

5. Assessment of Safety

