7.2.2. Feasibility Analysis Population

Non-evaluable subjects will be excluded from the feasibility analysis population. See Section 3.2 - Sample Size for definition of evaluable subject.

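### Does the protocol need a log, a repeat attestation and an evaluability rule for ECG leads that fall off during recording?

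*Combined protocol and SAP*

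**What the plan says.** Section 4.4 covers three situations during recording.

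- A lead falls off and the G4 shows no caution: "If an ECG lead should fall off during the data collection period, the lead can be replaced".
- A lead falls off and the G4 shows the caution: "If the caution indicator is displayed refrain from replacing the lead".
- The whole recording fails: "If the ECG stops recording during the data collection period, it will not be resumed".

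Placement is checked under Sections 4.3 and 4.3.1: "A second study team member will confirm and attest to the proper placement of the ecg lead", following the table of ten electrode sites. Sections 4.4.2 and 4.4.4 have the lead locations and the procedure start and stop times recorded. Neither lists a lead-off event.

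For a subject to be evaluable under Section 3.2, "data must be collected for the duration of the PICC insertion procedure on both the G4 and the ECG machines", together with the x-ray and the photographs. Section 3.2 adds: "Non-evaluable subjects will be replaced to meet the target sample size". Section 7.2.2 follows from it: "Non-evaluable subjects will be excluded from the feasibility analysis population". Section 4.6.3 tells the investigator to withdraw a subject "if any of the study procedures cannot be completed on the subject", and names the 12-lead ECG recording as one such procedure.

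**The concern.** The primary endpoint in Section 2.1 is successful collection of synchronized recordings, and Section 4.3.1 stresses consistent lead placement. Yet the protocol allows an electrode to be put back in mid-procedure without requiring a second check or a note of which lead it was and when. An electrode put back slightly off its site could alter the surface signal, and that could be mistaken for a real feature of the comparison with the intravascular ECG.

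The second worry is classification. With one lead off, the machine is still recording, which satisfies Section 3.2 literally. Someone might instead say that a 12-lead recording was not completed and withdraw the subject under Section 4.6.3. If the same recording can be counted, replaced or withdrawn, membership of the feasibility population could be settled after the data are seen, and the target of 20 might depend on the choice.

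**Working it through.** **Reading the passages together**

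1. Section 3.2 sets its test at machine level: both devices must have collected data throughout the insertion. It sets no condition on individual leads.
2. Section 4.4 separates a lead falling off, after which recording goes on, from the ECG stopping, after which it is not restarted. The first meets the Section 3.2 test. A stop before tip placement fails it.
3. Permission to replace a lead would serve little purpose if replacement made the subject non-evaluable. A replaced-lead recording therefore counts.
4. Section 4.6.3 concerns procedures that cannot be completed. A recording that runs through to tip placement has been completed. A conflict arises only if one missing lead is taken to mean non-completion, and no section says that.
5. The table in Section 4.3.1 governs any placement, including a replacement. What is missing is a required second verification; it does not follow that the lead is in a different place. Four of the ten electrodes (the limb electrodes) have broad permitted regions, so the point mainly concerns the six chest leads.

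**Size**

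The plan has no figure on this point to reproduce. Section 3.2 gives a cap of 30 enrolled and a target of 20 evaluable. The share of subjects with a lead-off event, *p*, is not in the documents, so I assume 5% to 30%. The 20 are treated as a single pool, and subjects as independent.

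- Chance that at least one of 20 is affected: 1 − (1 − *p*)^20. At *p* = 5% this is 1 − 0.95^20 = 64%.
- Strict reading (every affected subject non-evaluable, no other loss): P(Binomial(30, 1 − *p*) ≥ 20).
- Strict reading with a share *b* also lost for other reasons (assumed 10% or 20%): the evaluable probability becomes (1 − *b*)(1 − *p*). For example, 0.80 × 0.80 = 0.64.

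| Assumed *p* | At least 1 of 20 affected | Reach 20, strict, *b* = 0 | Strict, *b* = 10% | Strict, *b* = 20% |
|---|---|---|---|---|
| 5% | 64% | >99.9% | 99.8% | 92% |
| 10% | 88% | >99.9% | 98% | 81% |
| 20% | 99% | 97% | 81% | 46% |
| 30% | 99.9% | 73% | 42% | 16% |

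If affected recordings count, as steps 1 to 3 indicate, this cause removes nobody. The chance of reaching 20 is then above 99.9% at *b* = 10% and 97% at *b* = 20%, whatever *p* is.

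The reserve is 30 − 20 = 10 subjects. With no other loss, the expected evaluable number 30(1 − *p*) falls to 20 only at *p* = 1/3.

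**The case for a change.** The strongest case for a change is that feasibility here means whether these recordings are usable, so the definition of a usable recording is central. A lead left off while the caution indicator shows follows the protocol, so the deviation process in Section 9.2 would not pick it up. The trace may reveal that a lead was lost, but it cannot show where the electrode was put back. With 20% of subjects lost for other reasons and 20% affected, the chance of reaching 20 is 46% if affected subjects are excluded and 97% if they are counted. A few sentences and three or four case report form fields would close the gap.

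Part of this stands. The protocol does not require a log or a repeat check, and it does not say in words how a lead left off is treated. The position of a replaced chest lead is therefore not re-verified.

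The rest is weaker. The 46% needs two assumed rates and a reading of Section 3.2 that Section 4.4 argues against. Fear of selective counting belongs to a trial with a result to favour. Here Section 7.1 disclaims a statistical basis for the sample size, and Section 7.3 sets no test or threshold. The case report form is not among the documents, so it may already have a place for such events. Photographs do not add weight either: Sections 3.1, 3.2 and 4.3 disagree about who is photographed, and that is a separate question.

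**Conclusion.** No change is needed. This is missing operational detail that analysts can fill sensibly, and following the plan as written leads to no demonstrated wrong result. Recordings with a replaced lead remain evaluable when Sections 3.2 and 4.4 are read together. For a lead left off, the machine-level test still applies, and analysts can set aside the affected lead or segment. This rests on the expectation, which the documents do not state, that a lost lead is visible in the continuous digital trace sent to the sponsor.

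Even if every affected subject were excluded, the chance of reaching 20 evaluable is 97% or better at assumed rates of 5% to 20% with no other losses. It falls materially only if lead loss is more common or other attrition is also large. A shortfall below 20 would mean fewer recordings, but it would invalidate no inference, because none is planned. What remains is that a replaced chest lead is not checked a second time. That is a modest limitation for a single-centre feasibility data collection.
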